8.2 Venetoclax Dose Reduction and Re-Escalation Steps

The dose of venetoclax may be reduced. If administration of chemotherapy is delayed, the administration of Pola and R/SC should be delayed for the same timeframe; for example, if polatuzumab and rituximab and hyaluronidase are delayed, administration of venetoclax should also be delayed so that they are given together beginning on Day 1 of the same cycle.

For non-hematologic toxicities, dosing of Pola and R/SC may be resumed upon resolution to Grade 1 or baseline status. Resumption of dosing without complete resolution of toxicity may only be considered after careful weighing of the benefits and risks with the patient. A dose delay of 21 days is permitted for immunochemotherapy to allow recovery of hematologic toxicities to Grade 2 or non-hematologic toxicities to Grade 1 or baseline status for the first episode. Actions for recurrent hematologic adverse events are described in Table 8.31. If treatment is delayed for more than 3 weeks, the patient should be withdrawn from study treatment except in exceptional circumstances which may be discussed with the study chair. (NOTE: Lymphopenia is not considered a cytopenic toxicity, as it is an expected outcome of therapy). Patients who discontinue all study treatment for adverse events should proceed to clinical follow up and remain in the study.

The dose of venetoclax may be reduced according to the following dose reduction steps based on the starting dose.

Table 8.21: Venetoclax Dose Reduction Steps during Induction and Maintenance (Duration of Venetoclax in Maintenance is 1 year).

	Venetoclax Dose Reduction	
Starting Dose	Step 1	Step 2
(Dose 0)	(Dose -1)	(Dose -2)
400 mg	300mg	200mg
(days 1-21)	(days 1-21)	(days 1-21)
300mg	200mg	100mg
(days 1-21)	(days 1-21)	(days 1-21)
200mg	100mg	50mg
(days 1-21)	(days 1-21)	(days 1-21)
100mg	50mg	20mg
(days 1-21)	(days 1-21)	(days 1-21)
50mg (days 1-21)	20mg (days 1-21)	

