8.3 Toxicities during Induction Treatment

Table 8.31: Guidelines for Management of Hematologic Toxicities That Occur During Induction Treatment.

Heatment.					
Event	Action to Be Taken				
Grade 3 or	For patients who have had one or no prior venetoclax or polatuzumab vedotin				
4	dose reduction:				
Hematogic	• Withhold study treatment. ¹				
Toxicity ¹	 Administer RBCs or platelets as required. 				
	 If patient has not already initiated G-CSF, initiate prophylactic G-CSF for current and subsequent cycles. 				
	 Resume venetoclax and polatuzumab vedotin at same dose after interruption for 1st occurrence, once the toxicity has resolved to Grade 1 or baseline level 				
	 Resume venetoclax and polatuzumab vedotin at one level dose reduction after interruption for 2nd occurrence, once the toxicity has resolved to Grade 1 or baseline level. Refer to table 8.21 for dose reduction steps. 				
	• For patients who develop platelet count of 20,000/L while receiving LMWH, reduce the dose of LMWH. For patients who develop platelet count of 20,000/L while receiving platelet inhibitors, consider temporarily withholding platelet inhibitors.				
	No more than 2 dose level reductions in venetoclax and				
	polatuzumab vedotin are allowed during induction.				
	 Consider discontinuation of study drug for patients who require withholding study drug for more than 21 days. 				
	For patients who have had two prior venetoclax dose reductions:				
	 Permanently discontinue study treatment. 				
	 For grade 4 thrombocytopenia ≥ 7 days or grade 3 thrombocytopenia with ≥ grade 2 bleeding resume venetoclax and polatuzumab at one dose level dose reduction after the toxicity has resolved to Grade 1 or baseline level 				

(G-CSF) granulocyte colony-stimulating factor; (LMWH) low molecular weight heparin.

¹ Treatment delays apply to all toxicities; dose modifications apply only to toxicities that are considered to be related to any of the study treatment components. Toxicities that occur during the cycle and subside prior to the next cycle should not trigger the suggested dose modifications.

Table 8.32: Guidelines for Management of Non-Hematologic Toxicities That Occur During Induction

Table 8.32: Guide	elines for Management of Non-Hematologic Toxicities That Occur During Induction		
Event	Action to Be Taken		

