8.5 Management of Adverse Reactions for polatuzumab

Table 8.51 Management of Peripheral Neuropathy, Infusion-Related Reaction, and Myelosuppression

Table 8.51 Management of	Table 8.51 Management of Peripheral Neuropathy, Infusion-Related Reaction, and Myelosuppression				
Event	Dose Modification				
Grade 2–3 Peripheral Neuropathy	 Hold polatuzumab dosing until improvement to Grade 1 or lower. If recovered to Grade 1 or lower on or before Day 14, restart polatuzumab with the next cycle at a permanently reduced dose of 1.4 mg/kg. If a prior dose reduction to 1.4 mg/kg has occurred, discontinue polatuzumab. If not recovered to Grade 1 or lower on or before Day 14, discontinue polatuzumab. 				
Grade 4 Peripheral Neuropathy	Discontinue polatuzumab.				
Grade 1–3 Infusion- Related Reaction	 Interrupt polatuzumab infusion and give supportive treatment. For the first instance of Grade 3 wheezing, bronchospasm, or generalized urticaria, permanently discontinue polatuzumab. For recurrent Grade 2 wheezing or urticaria, or for recurrence of any Grade 3 symptoms, permanently discontinue polatuzumab. Otherwise, upon complete resolution of symptoms, infusion may be resumed at 50% of the rate achieved prior to interruption. In the absence of infusion related symptoms, the rate of infusion may be escalated in increments of 50 mg/hour every 30 minutes. For the next cycle, infuse polatuzumab over 90 minutes. If no infusion-related reaction occurs, subsequent infusions may be administered over 30 minutes. Administer premedication for all cycles. 				
Grade 4 Infusion- Related Reaction	 Stop polatuzumab infusion immediately. Give supportive treatment. Permanently discontinue polatuzumab. 				
Grade 3–4 Neutropenia ^{a,b}	 Hold all treatment until ANC recovers to greater than 1000/microliter. If ANC recovers to greater than 1000/microliter on or before Day 7, resume all treatment without any additional dose reductions. Consider granulocyte colony-stimulating factor prophylaxis for subsequent cycles, if not previously given. 				
Grade 3–4 Thrombocytopenia ^{a,b}	 Hold all treatment until platelets recover to greater than 75,000/microliter. If platelets recover to greater than 75,000/microliter on or before Day 7, resume all treatment without any additional dose reductions. 				
Infections and Infestations: Hepatitis Viral	Discontinue therapy and treat hepatitis				

^a Severity on Day 1 of any cycle.

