9.0 Ancillary Treatment/Supportive Care

- 9.1 Antiemetic's may be used at the discretion of the attending physician.
- 9.2 Blood products and growth factors should be utilized as clinically warranted and

^b If primary cause is due to lymphoma, dose delay or reduction may not be needed.

following institutional policies and recommendations. The use of growth factors should follow published guidelines of the American Society of Clinical Oncology (ASCO), Recommendations for the Use of WBC Growth Factors: American Society of Clinical Oncology Clinical Practice Guideline Update. J Clin Oncol 2015;33:3199-3212.

- 9.3 Patients should receive full supportive care while on this study. This includes blood product support, antibiotic treatment, and treatment of other newly diagnosed or concurrent medical conditions. All blood products and concomitant medications such as antidiarrheals, analgesics, and/or antiemetics received from the first day of study treatment administration until 30 days after the final dose will be recorded in the medical records.
- 9.4 Diarrhea: This could be managed conservatively with loperamide. The recommended dose of loperamide is 4 mg at first onset, followed by 2 mg every 2-4 hours until diarrhea free (maximum 16 mg/day).

In the event of grade 3 or 4 diarrhea, the following supportive measures are allowed: hydration, octreotide, and antidiarrheals.

If diarrhea is severe (requiring intravenous rehydration) and/or associated with fever or severe neutropenia (grade 3 or 4), broad-spectrum antibiotics must be prescribed. Patients with severe diarrhea or any diarrhea associated with severe nausea or vomiting should be hospitalized for intravenous hydration and correction of electrolyte imbalances.

- 9.5 Carriers of hepatitis B virus (HBV) should be closely monitored for clinical and laboratory signs of active HBV infection and for signs of hepatitis during and for up to several months following Rituxan therapy. In patients who develop viral hepatitis, Rituxan and any concomitant chemotherapy should be discontinued and appropriate treatment, including antiviral therapy, initiated. There are insufficient data regarding the safety of resuming Rituxan therapy in patients who develop hepatitis subsequent to HBV reactivation.
- 9.6 Prohibited Medications or Therapies
 - 9.61 CYP3A Inhibitors/Inducers

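### Tables 8.31 and 8.51 disagree on whether Day-1 Grade 3–4 neutropenia or thrombocytopenia caused by lymphoma requires a treatment hold, and on which day's count triggers one

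*Combined protocol and SAP*

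**What the plan says.** Table 8.31 (Section 8.3) covers Grade 3 or 4 hematologic toxicity during induction. Its first action is "Withhold study treatment", with venetoclax and polatuzumab vedotin resumed "once the toxicity has resolved to Grade 1 or baseline level". Footnote 1 states: "Treatment delays apply to all toxicities; dose modifications apply only to toxicities that are considered to be related" to a component of the regimen. For long holds the table says: "Consider discontinuation of study drug for patients who require withholding study drug for more than 21 days".

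Table 8.51 (Section 8.5) sits under a polatuzumab heading, but its neutropenia row says: "Hold all treatment until ANC recovers to greater than 1000/microliter". The thrombocytopenia row likewise holds all treatment, with a platelet threshold of 75,000 per microliter. Both rows carry two footnotes. Footnote a reads "Severity on Day 1 of any cycle". Footnote b reads "If primary cause is due to lymphoma, dose delay or reduction may not be needed".

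Section 8.2 states: "If treatment is delayed for more than 3 weeks, the patient should be withdrawn from study treatment". The sentence goes on to allow for exceptional circumstances, which may be discussed with the study chair.

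Under Sections 16.11 and 16.311, every eligible, consented patient who has begun treatment is evaluable for the primary endpoint unless classed as a major violation.

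**The concern.** The tables overlap. Polatuzumab is given on Day 1 of each induction cycle, so a Grade 3–4 neutrophil or platelet count on that day falls under both. When the count is low mainly because of lymphoma, Table 8.31 makes cause irrelevant to the hold and Table 8.51 makes cause a reason not to hold.

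The trial can enroll patients for whom this question arises: the growth-factor note in Section 7.713 refers to otherwise eligible patients with demonstrated marrow infiltration. If sites resolve the conflict differently, exposure to the regimen, and possibly continuation on it, will depend on which table a site opened. The primary endpoint is complete response at the end of a six-cycle induction in which all eligible treated patients count.

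**Working it through.** **1. The plan's own design figures.** Inputs from Sections 16.211 and 16.212: stop if 3 or fewer complete responses in 16; declare promising if at least 11 in 46. With p the true complete response rate,

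P(declare) = Σ over x = 4 to 16 of C(16, x) p^x (1 − p)^(16 − x) × P[Bin(30, p) ≥ max(0, 11 − x)].

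- p = 0.15: P(declare) = 0.0486; P(stop at interim) = 0.7899.
- p = 0.35: P(declare) = 0.8506; P(stop at interim) = 0.1339.

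These match the Section 16.24 table (0.049, 0.790, 0.851, 0.134). The dose-modification tables are not inputs, so the conflict changes none of them.

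**2. The two tables side by side.**

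| | Table 8.31 | Table 8.51, neutropenia and thrombocytopenia rows |
|---|---|---|
| Phase | Induction | Polatuzumab treatment, which is induction only |
| What is held | Study treatment | All treatment |
| Does cause matter to the hold? | No (footnote 1) | Yes; a delay may be unnecessary if lymphoma is the primary cause (footnote b) |
| Which count triggers it? | No day limit stated | Severity on Day 1 of a cycle (footnote a) |
| Level for resuming | Grade 1 or baseline | ANC above 1000, platelets above 75,000 per microliter |

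**3. A test case.** A patient has Grade 4 thrombocytopenia on Day 1 of cycle 3, judged to be due mainly to lymphoma. Under Table 8.31 all study treatment is withheld. Under Table 8.51 footnote b it may be given. A site that holds breaches neither table; a site that treats follows Table 8.51 and departs from Table 8.31.

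**4. Is there a rule of precedence?** Section 8.0 introduces the tables together and ranks none. The discretion it gives concerns additional dose reductions, not whether to delay. Table 8.32 footnote a repeats the all-causes principle for non-hematologic events.

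**5. The trigger day.** Section 7.4 requires a CBC every 7 days for the first 6 weeks, so mid-cycle Grade 3–4 counts can be seen. Table 8.31 would withhold for them; the Table 8.51 rows would not apply. The second sentence of footnote 1 exempts toxicities that subside before the next cycle from dose modification, but not from delay. After Day 1 only venetoclax is being dosed, so the mid-cycle difference falls on venetoclax.

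**6. From a hold to the endpoint.** Each link is conditional:

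- Hold to withdrawal: Section 8.2 needs a delay of more than 3 weeks and no exception. Table 8.31 says only to consider discontinuation after 21 days. The mandatory 21-day rule in Table 8.32 is confined to toxicity attributable to study treatment and sits in the non-hematologic table.
- Withdrawal to endpoint: the patient remains evaluable, so the denominator is unchanged. One patient who would have been a complete response and is not moves the observed rate by 1/46 = 0.0217, or 2.2 percentage points.
- Number of such patients: not given, and not derivable from the documents.

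**The case against.** The strongest reply is that footnote b is permissive and specific, and so reads naturally as an exception to a general rule. That reading is reasonable, but no passage states it, and footnote 1 says delays cover all toxicities. Nor can Table 8.51 be set aside as polatuzumab-only, because the two rows hold the whole regimen.

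The objections to large consequences do stand. A reader might infer that patients with marrow disease are held and then withdrawn under Table 8.31. The documents do not support that. Table 8.31 asks only for discontinuation to be considered, Section 8.2 has the study-chair route, and Section 8.2 also permits a first-episode delay for hematologic recovery to Grade 2, a looser level than in Table 8.31. Table 8.31 adds G-CSF and transfusion, and Section 7.713 allows prophylactic growth factor when the marrow is infiltrated.

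Eligibility narrows the group further. Section 3.15 requires ANC of at least 1000 and platelets of at least 75,000 for everyone, the same numbers Table 8.51 uses for recovery, and Section 3.0 bars waivers. Patients already below those counts from marrow disease are not enrolled. What remains is patients whose counts fall after registration for a reason judged to be lymphoma, and if that is progression, Section 13.0 sends them to survival follow-up whichever table is used.

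A reader might also infer a quantified loss of power. That would need the number of patients withdrawn this way and their chance of response, and the documents give neither.

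**Conclusion.** The contradiction is real but narrow. It concerns Grade 3–4 neutropenia or thrombocytopenia on Day 1 of an induction cycle with lymphoma as the primary cause, plus a separate mismatch over whether mid-cycle counts trigger a hold. Sites can hold or treat the same patient differently and each point to the protocol. The possible effect on the primary result is at most 2.2 points per affected patient. It arises only if a hold passes 3 weeks, no exception is made, and a complete response is lost as a result. How many patients this could involve is unknown, the Section 16.24 operating characteristics stand as written, and no power figure should be attached. The passages should be reconciled because they give opposite instructions for the same event, not because a measurable bias has been shown.

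**What to change.** Reconcile Table 8.31 footnote 1, Table 8.51 footnotes a and b, and the delay limit in Section 8.2. State once, and cross-refer from both tables:

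- which table prevails where they overlap;
- whether neutropenia or thrombocytopenia attributed primarily to lymphoma is exempt from the hold, and separately from the delay limit;
- who makes that attribution and on what evidence;
- whether the trigger is the Day-1 count or any count.

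The clinical choice on each is for the study chair; this review takes no position.

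The cost is mainly footnote wording. The CBC schedule already supplies the counts. Attribution needs more thought: under the Section 4.0 schedule a negative baseline marrow may be up to 90 days old at registration and a positive one older, and the marrow is repeated only to confirm an end-of-induction complete response. The baseline result alone therefore cannot settle the cause of a low count during induction, and the amended text should say what can be relied on.

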Agent	Dose	Route	Day
Dexamethasone ¹	10-20 mg	IV or PO	Within 1 hour of R/ScHyc/Pola
Acetaminophen ¹	650mg	PO	Within 1 hour of R/ScHyc/Pola
Benadryl ¹ and	25-50 mg		
Ranitidine or	50 mg	IV^2	30 minutes prior to R/ScHyc/Pola
Cimetidine or	300 mg		
Famotidine	20 mg		
Allopurinol	100mg	PO	Three times daily from day 1 of cycle 1 to day 1 of cycle 3.

Acyclovir	400mg	PO	Twice daily
Bactrim DS	1 tablet three times a week	oral	Continuously during treatment. Monday/Wednesday/Friday

- 1. If taken within 8 hours of Rituximab and polatuzumab, each premedication will only need to be taken once per cycle
- 2. Benadryl can be taken PO or IV

7.2 Induction (Cycles 1-6):

- Patients will receive rituximab 375mg/m² IV on day 1 of cycle 1, and rituximab and hyaluronidase human SQ day 1 of cycles 2-6
- Patients will receive polatuzumab vedotin 1.8 mg/kg IV on Day 1 of each 21-day cycle for a total of 6 cycles.
- Patients will receive venetoclax PO 20 mg beginning on day 1 of cycle 1. On day 7 of cycle 1 they will begin ramp-up increasing over 5 weeks to 400 mg po daily days 1-21 cycles 1-6. If not tolerated venetoclax will be dose reduced.
- Missed/skipped/vomited doses will not be made up (i.e. the patient should not double their dose if the previous dose was missed).
- For first infusion only, vital signs to be collected prior to dosing, every 15 minutes (+/- 5 minutes) during dosing and 30 minutes (+/- 10 minutes) after treatment completion until vital signs normalize or return to baseline. For vital signs that are normal/return to baseline at the 30 minutes (+/-10 minutes) assessment, no additional vitals are required. For subsequent infusions, vital signs should be collected prior to dosing and every 30 minutes (+/- 10 minutes) during dosing. After treatment completion: Patients who have never had a documented infusion reaction, post-dosing vital signs may be obtained at 30 minutes post infusion for the second infusion, and thereafter at 15 minutes aftertreatment completion. Additionally, O2 should be monitored as a vital sign during each visit. In cycle 1, if the investigator feels that the patient is at significant risk of tumor lysis, patients should be monitored for tumor lysis per institutional standard.
- When study treatments are given on the same day, they will be administered sequentially in the following order:

Order of Administration (See section 15 for individual drug instructions)

- 1) Venetoclax[#] (No time constraints)

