7.7 Definitions of significant toxicity

- 7.71 Toxicity will be measured per NCI-CTCAE version 5. For this protocol, significant toxicity will be defined as an adverse event occurring during the first 3 cycles of treatment that is possibly, probably, or definitely related as follows: NOTE: All significant non-hematologic toxicities must be resolved to a minimum of grade 1 for ongoing treatment at any cycle of treatment.
 - 7.711 Non-Hematological significant toxicities. Any Grade 3 or Grade 4 non-hematological toxicity that is possibly, probably or definitely attributable to the regimen of RSC+Pola+Ven is considered a significant toxicity, including the following:
 - Non-hematologic toxicity that causes a delay of >14 days in initiating cycle 2.
 - Any type of grade 3-4 hypersensitivity reaction (i.e.: allergic reaction, anaphylaxis, serum sickness, skin disorders, etc.), regardless of attribution, that necessitate discontinuation of study drug.
 - Any type of grade 3-4 immune related adverse event or immune system disorder including skin reactions.
 - Grade 3 or greater colitis and bowel perforation
 - Grade 3 ALT/AST elevation
 - Grade 3 or greater TLS

NOTE: The following events are exclusions and are NOT considered a significant toxicity for this protocol, regardless of attribution or specific type:

• Grade 3 nausea, vomiting, diarrhea, or oral mucositis with < 3 days

duration.

- Grade 3 fever.
- Grade 3 peripheral sensory neuropathy that is decreased by at least one grade within 7 days.
- Grade 3 hypophosphatemia, hypokalemia, hypocalcemia or hypomagnesemia responsive (i.e.: decreased by at least one grade) to oral supplementation within 7 days.
- Grade 3 hypertriglyceridemia that returns to < Grade 2 prior to the beginning of cycle 2.
- Grade 3 hyperglycemia that returns to < Grade 2 (with or without the use of insulin or oral diabetic agents) prior to the beginning of cycle 2.
- 7.713 Hematological significant toxicity. The following hematological toxicity possibly, probably or definitely attributable to the regimen of RSC+Pola+Ven is considered a significant toxicity:
 - Grade 4 neutropenia for > 7 days without growth factor support
 - Grade 4 febrile neutropenia
 - **NOTE:** Grade 4 non-febrile neutropenia will not be a significant toxicity but should warrant growth factor support on subsequent doses.
 - Platelet count < 25,000/uL on 2 separate days, or requiring a platelet transfusion on 2 separate days within a 7-day period

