8.0 Dosage Modification Based on Adverse Events

Dose modification guidelines are provided specifically for venetoclax, polatuzumab vedotin, rituximab, and rituximab/hyaluronidase human in the tables below. In addition, Venetoclax dose reductions will be discussed in Section 8.21.

If the patient requires a dose reduction, no dose re-escalation (e.g. no return to the baseline dose) is permitted.

Additional dose reductions may be employed at investigator discretion as clinically appropriate to ensure patient safety, and exact modification, timing, and reasons should be recorded.

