Infections and Infestations; AE: Hepatitis viral	Discontinue therapy and treat hepatitis		

Table 8.32: Guidelines for Management of Non-Hematologic Toxicities That Occur During Induction (cont.)

Event	Grade	Action to Be Taken	
Peripheral Neuropathy	Grade 4	Permanently discontinue polatuzumab vedotin and all other study treatment.	
	Grade 2	1. Delay study treatment. a	
	or 3	2. If improvement to Grade 1 within 21 days, resume study treatment for current and subsequent cycles as follows:	
		a. Resume rituximab or rituximab and hyaluronidase human at full dose	
		b. Resume venetoclax at current dose ^a	
		c. For patients who started at 1.8 mg/kg, resume polatuzumab vedotin at the permanently reduced dose of 1.4 mg/kg;	
Other non-hematologic toxicities (i.e., not described above), excluding alopecia, nausea, and vomiting	Grade 3 or 4	 dose of 1.4 mg/kg; For patients who have had no prior dose reductions: Withhold study treatment.^a If improvement to Grade 1 or baseline, resume rituximab and polatuzumab vedotin at full dose and resume venetoclax at next lower dose ^a for current and subsequent cycles perguidelines. For patients who have had one prior dose reduction: Grade 4 events Permanently discontinue study treatment. Grade 3 events Withhold study treatment.^a If improvement to Grade 1 or baseline, rituximab and polatuzumab vedotin at full dose and resume venetoclax at next lower dose ^a for current and subsequent cycles per guidelines. No more than two dose level reductions from the original dose of venetoclax are allowed during induction. For patients who have had two prior dose reductions: Permanently discontinue study treatment. 	
	Grade 2	 Withhold study treatment.^a If improvement to Grade 1 or baseline, resume rituximab and polatuzumab vedotin, and venetoclax at full dose. 	

IRR-infusion-related reaction; PML-progressive multifocal leukoencephalopathy; TLS-tumor lysis syndrome; ULN-upper limit normal.

^a Treatment delays apply to all events; dose modifications apply only to events that are considered to be related to any of the study treatment components. Toxicities that occur during the cycle and subside prior to the next cycle should not trigger the suggested dose modifications.

8.4 Toxicities during Maintenance Treatment provides guidelines for management of toxicities that occur during maintenance treatment.

Table 8.43: Guidelines for Management of Toxicities That Occur during Maintenance Treatment

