Hypotension, bronchospasms, and angioedema have occurred in association with Rituxan infusion. Because of this it is recommended that patients be pre-medicated with acetaminophen and diphenhydramine before infusion. Stop infusion for severe reaction. Infusion may be restarted at 50% rate after resolution of symptoms. It is recommended that diphenhydramine, acetaminophen, epinephrine, bronchodilators, IV saline, and corticosteroids are available for immediate use in the event of a hypersensitivity reaction during administration.

Patients should be cautioned to withhold their anti-hypertensive medication for 12 hours prior to drug administration.

Patients with preexisting cardiac conditions including arrhythmias and angina have had recurrences of these events during Rituxan therapy and should be monitored throughout the infusion and immediate post-infusion period.

It has been found that patients with bulky disease (lesion >10 cm in diameter) have an increased incidence of adverse events. Monitor for signs and symptoms of tumor lysis syndrome, and acute renal failure.

An infusion-related symptom complex consisting of fever and chills/rigors occurs in the majority of patients during the first infusion. These reactions generally occur within 30 minutes to 2 hours of beginning the first infusion and resolve with slowing or stopping the infusion and giving supportive care. The incidence of adverse reactions decreased from 80% to 40% with subsequent infusions.

Cytopenias are common and can be long term. Monitor CBC. Instruct patient to report signs and symptoms of infection, excessive bruising and/or bleeding to the health care team.

GI disturbances (Nausea, abdominal pain and less commonly diarrhea, vomiting, dyspepsia) headache, and weakness are common side effects. Treat as necessary. Monitor for effectiveness.

Adequate birth control measures should be used during therapy and for 12 months following therapy. Women should not breastfeed while drug is detectable in serum.

15.49c Endocrine and metabolic disturbances can be seen (hyper/hypoglycemia, hypocalcemia, hypocholesterolemia, hyperphosphatemia, hyperuricemia. Monitor labs and for signs or symptoms of these conditions. Treat accordingly.

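### As extracted, the plan sets no reaction grade that permanently stops rituximab, and the default row of Table 8.32 resumes it at full dose after a grade 4 reaction in a patient with no prior dose reduction

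*Combined protocol and SAP*

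**What the plan says.** - Section 8.0 sets the expectation: "Dose modification guidelines are provided specifically for venetoclax, polatuzumab vedotin, rituximab, and rituximab/hyaluronidase human in the tables below".
- Table 8.32 (induction, non-hematologic) has a residual row for toxicities that no other row describes. For a grade 3 or 4 event with no prior dose reduction, treatment is held and then: "If improvement to Grade 1 or baseline, resume rituximab and polatuzumab vedotin at full dose and resume venetoclax at next lower dose". After one prior reduction, a grade 4 event ends study treatment. After two, any grade 3 or 4 event does.
- Footnote a to that table: "Toxicities that occur during the cycle and subside prior to the next cycle should not trigger the suggested dose modifications".
- The same table for grade 4 peripheral neuropathy: "Permanently discontinue polatuzumab vedotin and all other study treatment".
- Table 8.51 sits in the section on polatuzumab reactions. For a grade 4 infusion reaction it begins "Stop polatuzumab infusion immediately" and goes on to end polatuzumab for good. Rituximab is not named.
- Section 7.2 (order of administration) points sites onward: "See section 15 for individual drug instructions". Section 15.44 then tells them to slow or stop rituximab for a reaction and restart at half the rate. Section 15.49b says: "Stop infusion for severe reaction. Infusion may be restarted at 50% rate after resolution of symptoms". Neither gives a grade.
- Section 7.711 counts as significant toxicity grade 3-4 hypersensitivity reactions, "regardless of attribution, that necessitate discontinuation of study drug". It does not say which reactions those are.

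**The concern.** Section 8.0 promises rituximab rules, and the protocol treats severe rituximab reactions as serious. Exclusion 3.29g keeps out anyone with a past severe allergy or anaphylaxis to rituximab, and Section 15.47 refers to the boxed warning on infusion reactions. Yet a patient who has a grade 4 rituximab reaction on study falls under a general row whose instruction is to give rituximab again at full dose. If any dose is cut, it is that of venetoclax, which did not cause the event. At stake is re-exposure after a life-threatening reaction, and sites deciding differently on when to stop. If a site does stop rituximab, the plan also does not say whether the other two drugs go on.

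**Working it through.** No formula applies apart from a dose count. The check is which rule governs a grade 4 rituximab reaction and what it leads to.

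**Step 1: which row applies.** As extracted, Table 8.32 has rows for general delays, tumor lysis, PML, liver tests, viral hepatitis, peripheral neuropathy and other non-hematologic toxicities. None is for an infusion or hypersensitivity reaction. The Table 8.51 reaction rows interrupt, stop or slow polatuzumab only. Where that table means every drug it says so: its neutropenia and thrombocytopenia rows hold all treatment. A rituximab reaction therefore lands in the residual row of Table 8.32.

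**Step 2: what that row does after a grade 4 event.**

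| Prior dose reductions | Event subsided before next cycle? | Rituximab | Venetoclax |
|---|---|---|---|
| None | Yes (footnote a) | Full dose | Unchanged |
| None | No, recovers later | Full dose | One level lower |
| One or two | Either | Permanent stop | Permanent stop |

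At cycle 1 day 1, the first rituximab exposure on study, no patient has a prior reduction, so only the first two lines are open. Both bring rituximab back at full dose. The second is narrow: the general row of Table 8.32 ends study treatment when an attributable toxicity keeps it on hold for 21 days, and one cycle is 21 days, so its reach depends on how the hold is counted.

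**Step 3: whether another section sets a limit.**

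- Section 15.44: slow or stop, then restart at 50% of the rate. No grade.
- Section 15.49b: stop for a severe reaction, restart allowed at 50%. No upper grade.
- Section 7.711: foresees discontinuation after grade 3-4 hypersensitivity, but does not say when it is required.
- Section 13.72 and the package-insert reference in Section 15.4: leave the stop to judgement and labelling.
- Table 8.43 (maintenance): as extracted, the only graded non-hematologic row is grade 2, so it gives no rule for a grade 3 or 4 reaction.

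**Step 4: exposure still scheduled.** Doses come from Tables 7.2a and 7.3 (footnote 1).

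- Total: 1 IV (cycle 1) + 5 subcutaneous (cycles 2-6) + 6 subcutaneous (maintenance) = 12.
- After a reaction at cycle 1 day 1: 12 − 1 = 11 remain, 5 in induction and 6 in maintenance.

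**Step 5: the plan's own comparator.** For polatuzumab, Table 8.51 orders a permanent stop at grade 4, at a first grade 3 bronchospasm, generalized urticaria or wheezing, when any grade 3 symptom recurs, and when grade 2 wheezing or urticaria recurs. Rituximab has no counterpart to any of these.

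**The case against.** The strongest reply is that the row may exist. The Table 8.32 key defines IRR, no extracted row uses the term, and the table is visibly damaged: a fragment of the neuropathy row reappears inside the residual row. Content lost in reading the PDF is not a fault in the plan. A leftover abbreviation is also possible, because a source line after Table 8.44 shows text carried over from another protocol. The documents cannot settle which it is. This stands, and it makes the point conditional.

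The second reply is that the tables are guidelines. Section 13.72 removes a patient whose safety is in jeopardy, Section 7.711 foresees discontinuation, and the package insert is referenced. A careful investigator would probably stop rituximab. That lowers the likely harm, but the written default still points the other way, and a discretionary clause does not correct it.

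Several stronger readings are tempting, and the documents do not support them:

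- *That no grade of any event stops rituximab.* Grade 4 neuropathy, and a grade 4 residual-row event after one prior reduction, stop all study treatment. Only a rule specific to rituximab reactions is absent.
- *That any first grade 4 reaction leads to re-exposure.* The row turns on prior dose reductions. A first reaction after an earlier reduction ends treatment.
- *That venetoclax is routinely cut for a rituximab reaction.* Footnote a spares it if the event subsides before the next cycle, as an acute reaction usually would (an assumption).
- *That Table 8.43 repeats the fault in maintenance.* As extracted it is silent at grade 3-4.
- *That the undefined tolerance condition for the subcutaneous switch is a defect of the same weight.* Table 7.2a already requires a full IV dose to be both received and tolerated, and Section 15.44 lets some patients with a mild reaction stay on IV. The rest is mostly wording.

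**Conclusion.** The concern holds in this limited form, provided the protocol PDF contains no reaction row for rituximab. No rule sets the grade of rituximab infusion-related or hypersensitivity reaction that permanently ends the drug. The default that fills the gap resumes full-dose rituximab after grade 4 in a patient with no prior dose reduction. This is more than missing detail, because a stated instruction gives an unsafe result and sits badly with exclusion 3.29g and with the grade 4 polatuzumab stop. The misplaced venetoclax reduction is secondary and arises only if the event has not subsided before the next cycle.

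The size cannot be put in patients, because the documents give no rate of grade 4 rituximab reactions. The 11 remaining doses describe one patient's scheduled exposure and are not an estimate of harm. No effect on power, type I error or the primary endpoint is claimed. Confidence is medium because of the possible lost row. If one is found, what remains is the restart in Section 15.49b without an upper grade.

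**What to change.** 1. Check the protocol PDF for an IRR row in Table 8.32.
2. If there is none, add a row for rituximab infusion reaction and anaphylaxis, cross-referenced in Table 8.43, that:
   - permanently stops rituximab, IV and subcutaneous, after a grade 4 infusion-related or anaphylactic reaction;
   - treats grade 3 at least as strictly as Table 8.51: permanent stop at a first grade 3 bronchospasm, generalized urticaria or wheezing, or when any grade 3 symptom recurs; otherwise slow or stop and restart at 50%. A restart after every grade 3 reaction would be looser than the polatuzumab rule;
   - does not reduce venetoclax for such a reaction;
   - states whether polatuzumab and venetoclax continue once rituximab is stopped. This is the sponsor's decision, and the plan's precedents differ: for grade 4 neuropathy Table 8.51 stops polatuzumab, while Table 8.32 stops everything.
3. Limit the restart in Section 15.49b to reactions below grade 4.

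Optional: align Sections 15.34 and 15.39 with the received-and-tolerated condition in Table 7.2a. If tolerance is defined, keep the Section 15.44 option for mild reactors to stay on IV; a definition based only on grade 3-4 events could move them to subcutaneous dosing sooner.

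Cost: one table row, one cross-reference and one amended sentence. Sample size, endpoint and decision rule stay as they are. The downside is that a rare patient loses rituximab.
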